### **11a. Measurement tools used**

The survey will be designed in stage 1.  
Initial items are described above and in the Appendix A.

### **11b. Data monitoring**

No identifiable information will be collected.

The anonymous data will be transferred in password protected files between collaborators. All collaborating organizations are based in the United Kingdom

The survey will be set up to ensure complete data collection, by reminding participants who forget to answer an item to do so before they advance in the survey. If participants do not wish to answer an item, they can withdraw by simply closing their browser window. Incomplete surveys will not be analyzed.

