Appendix A also includes three self-confidence items.

The first item regards participants' confidence about how often their children clean their hands when they are present, 0% to 100% of the time. The second item regards participants' confidence about how often their children clean their hands when they are not present, 0% to 100% of the time. The third item regards participants' confidence about how often they clean their own hands, 0% to 100% of the time.

*Translation.*

After creating the initial items in the English language, the research team will ask OpinionHealth to translate them. The same process will occur for the information/consent sheet. The translation process will proceed as describe in Table 1.

Table 1. Translation process

Step	Action
1	The research team will provide OpinionHealth with the initial items.
2	OpinionHealth will translate the items into the non-English language(s)
3	OpinionHealth will back-translate the items to English.
4	OpinionHealth will provide the research team with copies of the translated and back-translated items.
5	The research team will check to be sure that the items' intended meanings have not been lost in translation. If items' meaning are lost, the translation process will be repeated with those items.

---

Opinion is a reputable survey company located in the United Kingdom experienced in conducting online surveys in line with all UK and EU regulations and Market Research Society's Code of Conduct, e.g., GDPR. For more information, a link to Opinion Health's website is provided here:  
[http://opinionhealth.com/about\\_us](http://opinionhealth.com/about_us)

*Active survey.*

OpinionHealth will to recruit participants according to a stratified fashion across countries and demographic characteristics, see Table 2.

Table 2. Participants stratified characteristic

Country	Participants
India	375 mums 375 dads 75 teachers
UK	225 mums 225 dads 75 teachers
China	225 mums 225 dads 75 teachers
Australia	225 mums 225 dads 75 teachers
South Africa	225 mums 225 dads 75 teachers
Indonesia	225 mums 225 dads 75 teachers
Saudi Arabia	225 mums 225 dads 75 teachers

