The first screen of the online survey will inform participants of the study and request their informed consent to take part (see Appendix B). Those who give their informed consent will continue. Participants who complete the survey will be issued with payment to compensate them for their time in an amount equal to approximately 1 GBP in their home countries currency (varies depending on exchange rates), which they can redeem in the form of amazon gift vouchers or via their personal PayPal accounts.

We will stop collecting survey responses in each country after the planned-sample sizes are achieved or 30 days have passed since that country's survey was activated, whichever comes first.

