Appendix A. Survey items (finalized 09-Apr-2020)

Domain	Question Number	Handwashing Surface Disinfection	Parents	Teachers
Knowledge An awareness of the existence of something	1	H	I know that my children should wash their hands with soap and water for at least 20 seconds.	I know that my pupils should wash their hands with soap and water for at least 20 seconds.
	2	H	(RS) I do not know when my children should wash their hands with soap and water.	(RS) I do not know when my pupils should wash their hands with soap and water.
	3	H	(RS) I know that when my children's hands look clean, they are germ free.	(RS) I know that when my pupils hands look clean, they are germ free.
	4	SD	(RS) I know that when surfaces look clean, there are no germs.	(RS) I know that when surfaces look clean, there are no germs.
	5	SD	I know which surfaces I should disinfect in the home.	I know which surfaces I should disinfect in the classroom
Skills An ability or proficiency acquired through practice	6	H	I am able to teach my children to wash their hands.	I am able to teach my pupils to wash their hands.
	7	H	I am able to help my children develop good handwashing habits.	I am able to help my pupils develop good handwashing habits.
	8	H	(RS) I am not able to teach my children to wash their hands.	(RS) I am not able to teach my pupils to wash their hands.
	9	SD	I have the ability to disinfect surfaces in the home.	I have the ability to disinfect surfaces in the classroom
	10	SD	(RS) I do not have the ability to disinfect some of the surfaces in the home.	(RS) I do not have the ability to disinfect some of the surfaces in the classroom
Memory, attention and decision processes The ability to retain information, focus selectively on aspects of the environment and choose between two or more alternatives	11	H	I remind my children to wash their hands before eating.	I remind my pupils to wash their hands before eating.
	12	H	(RS) I forget to remind my children to wash their hands.	(RS) I forget to remind my pupils to wash their hands.
	13	H	(RS) There are many distractions that cause me to forget to remind my children to wash their hands.	(RS) There are many distractions that cause me to forget to remind my pupils to wash their hands.
	14	SD	I remember to disinfect the surface areas in my home every day.	I remember to disinfect the surface areas in the classroom every day.

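### The plan sets no screen for constant answering in a paid survey where every item must be answered, and a small share of off-midpoint straight-liners could make a correct 11-factor model miss its fit criteria

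*Combined protocol and SAP*

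**What the plan says.** Section 11b handles data quality through completeness. The survey works by "reminding participants who forget to answer an item to do so before they advance in the survey". The stated alternative to answering is to leave: "If participants do not wish to answer an item, they can withdraw by simply closing their browser window". Then: "Incomplete surveys will not be analyzed".

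Section 11 (Active survey) ties payment to finishing: "Participants who complete the survey will be issued with payment to compensate them for their time in an amount equal to approximately 1 GBP". A survey company recruits to quotas by country and by mums, dads and teachers (Table 2).

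Section 11 (Survey Section 3) contains two design safeguards. Some items are reverse scored to reduce acquiescence bias, and items appear in random order. Appendix A marks the reversed items. For example, item 8, "I am not able to teach my children to wash their hands", negates item 6. No section uses such pairs to identify or exclude anyone.

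Section 12b judges the primary CFA by chi-square/df below 2, RMSEA close to or below 0.06, and a comparative index close to 0.95. It allows the models to be revised until fit is reached. Alpha should reach 0.70 in each domain, with 0.65 tolerated.

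**The concern.** A respondent who clicks the same option from start to finish submits a complete survey, is paid, and is removed by nothing in the plan. On a scale with mixed directions such a record contradicts itself. After reverse scoring it adds covariance among reversed items across all domains, which an 11-factor model has no term for.

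The primary hypothesis is that the TDF domains describe the hand-hygiene data well, judged by these fit indices. If the first fit is poor because of a few such records, the plan's response is to revise the model. The published structure could then partly describe inattentive answering, and a reader could not tell. If the rate differs between countries, the country models would differ for the same reason. The domain averages also feed the Objective 3 regressions. An all-5 respondent averages (5 + 1 + 1)/3 = 2.33 in the six domains with two reversed items and (5 + 5 + 1)/3 = 3.67 in the other five.

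**Working it through.** **Inputs from the documents**
- Sample (Table 2): India 375 + 375 + 75 = 825; six other countries 225 + 225 + 75 = 525 each; pooled 825 + 6 × 525 = 3,975.
- Items (Appendix A): 11 domains × 3 = 33 hand-hygiene items. Reversed items by domain, in order: 2, 1, 2, 2, 2, 1, 2, 1, 2, 1, 1, a total of 17. Every domain mixes directions.
- Model: 33 loadings + 33 residual variances + 55 factor covariances = 121 parameters; df = 33 × 34/2 − 121 = 561 − 121 = 440.

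**The plan's own figure.** Section 12a asks for 10 to 20 participants per parameter: 1,210 to 2,420. The pooled sample gives 3,975/121 = 32.9, so the rule is met there. It does not address data quality.

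**Assumptions (not in the documents).** A true 11-factor model; loadings 0.66 to 0.8; factor correlation 0.5; item SD 0.9; three sets of scored item means (all 4.2; varying from 3.2 to 4.7; forward items 4.4 with reversed items 3.6). A share e = 3% (0.03 × 3,975 = 119 people) gives one raw answer c to all items, scored 6 − c on reversed items.

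**Mechanism, by hand** (means 4.2, loading 0.7). Among attentive respondents every cross-domain covariance is 0.5 × 0.49 × 0.81 = 0.198, or 0.192 after weighting by 0.97. Straight-liners spread over 3, 4 and 5 average 4 on forward items and 2 on reversed ones, which is −0.2 and −2.2 from the attentive mean. The variance of c is 2/3. With e(1 − e) = 0.0291, the covariances become:
- reversed with reversed: 0.192 + 0.03 × 0.667 + 0.0291 × 4.84 = 0.353
- forward with forward: 0.192 + 0.020 + 0.0291 × 0.04 = 0.213
- forward with reversed: 0.192 − 0.020 + 0.0291 × 0.44 = 0.185

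One correlation per pair of factors cannot reproduce all three. If everyone in the 3% answers 3, the shift is −1.2 on every item, and all covariances rise by the same 0.0291 × 1.44 = 0.042. The factors absorb that, so fit survives.

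**Fit of the correct model at 3%.** Maximum-likelihood CFA on the mixture covariance gives the minimum discrepancy F. Then chi-square/df = 1 + (N − 1)F/440, RMSEA = √(F/440), CFI = 1 − F/F_baseline. Ranges run over the loadings and mean sets. A pooled chi-square/df of r becomes 1 + (r − 1) × 524/3,974 at N = 525.

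| Constant answers | chi-square/df, N = 3,975 | chi-square/df, N = 525 | RMSEA | CFI |
|---|---|---|---|---|
| 1 to 5 evenly | 19.5–32.6 | 3.4–5.2 | 0.068–0.089 | 0.79–0.83 |
| 3, 4, 5 evenly | 8.3–27.0 | 2.0–4.4 | 0.043–0.081 | 0.83–0.92 |
| 2, 3, 4 evenly | 5.2–11.1 | 1.6–2.3 | 0.033–0.050 | 0.93–0.95 |
| all 4 | 2.3–17.0 | 1.2–3.1 | 0.018–0.063 | 0.90–0.985 |
| all 5 | 20.7–56.1 | 3.6–8.3 | 0.070–0.118 | 0.68–0.80 |
| 80% at 3, 20% at 4 | 1.5–3.3 | 1.1–1.3 | up to 0.024 | 0.985 or more |
| all 3 | 1.0–1.8 | at most 1.1 | up to 0.014 | 0.995 or more |

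For the 3, 4, 5 pattern, pooled chi-square/df reaches 2 at a share of 0.3% to 0.8%, which is 12 to 32 people. A separate simulation of that pattern at 3% gave chi-square/df 2.6 and CFI 0.87 at N = 525, 11.9 and 0.88 at N = 3,975, and RMSEA 0.052 to 0.055.

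**Alpha.** In simulation, mean alpha moved from 0.70 to 0.69 at 3% and to 0.65 at 10%. Single domains can move more: at loading 0.7 with varying means, the lowest fell from 0.742 to 0.679, still above the 0.65 floor.

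**With no straight-liners.** Simulated 5-point data at N = 3,975 gave chi-square/df 0.98 to 1.08, RMSEA at most 0.004 and CFI at least 0.998.

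**The case against.** A reader might infer that 3% of careless respondents would make the primary analysis fail. The documents do not support that. They state neither a rate nor a pattern, and the pattern decides the result: midpoint-only answering passes all three criteria, and mostly-midpoint answering passes or narrowly misses one. RMSEA passes in many off-midpoint cases. A poor first fit also leads to revision, not to a negative conclusion.

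A reader might also infer that the alpha rule would force items out. The average change is about 0.01, and 0.65 is tolerated.

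Part of the pooled excess comes from the criterion. At N = 3,975, chi-square/df below 2 means RMSEA below √(1/3,974) = 0.016, so slight misfit of any kind breaches it. That stands. It does not explain the CFI loss, since CFI as computed here does not depend on N.

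Reverse scoring and random order are genuine safeguards and deserve credit. They keep constant agreement from raising every domain score, but they do not remove the records. That every complete survey is analysed is an inference from silence. The survey company may screen, but the plan does not say so or fix a rule common to all countries.

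**Conclusion.** The gap is real and its consequence conditional. The plan has no screen for constant answering, although items must be answered and completion is paid. Assuming 3% constant answers spread over 3, 4 and 5, a correct pooled model would clearly miss chi-square/df and fall short on CFI. A country model of 525 would lie from the chi-square/df limit to about twice it. RMSEA could go either way. The size rests on the assumed share, pattern, loadings and item means, none of which the documents give; the effect on the regressions was not quantified. The main harm is that open-ended revision could change a correct structure to fit a response artefact. An exclusion chosen later would be chosen with the fit in view.

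**What to change.** Add to section 12b, before data are seen:
- Respondents giving the same raw answer to all 33 hand-hygiene items are excluded from the CFA and the regressions.
- Their number is reported by country.
- The primary CFA is repeated with them included.
- Agreement with both items 6 and 8 is used only as a further sensitivity exclusion. These are two of the three Skills indicators, so selecting on them in the main analysis would favour the fit being tested.

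This costs one filter on data already planned and one or two repeat runs; the survey does not change. At a 3% rate about 3,856 of 3,975 records would remain (3,975 − 119). The downsides are that small loss, the possible loss of a few genuinely neutral respondents who answer 3 throughout, and no protection against near-constant or random answering. The repeat run shows how much the exclusion matters.

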## **12. Statistical Considerations and Data Analysis**

### **12a. Sample size and statistical power**

The sample-size is designed to support a factor analysis and regression analysis for the hand-hygiene component of the project. The surface cleaning component of the project will be analyzed using descriptive and exploratory methods.

The planned sample size is given in Table 2.

As per standard practice, each domain in the final survey will be captured by at least three items. In addition, a general rule of thumb recommends that collecting responses from 10 to 20 participants for each parameter in the hypothesized model with at least 100 participants in each sub-group. Our planned samples size meets these criteria, with the exception of teachers and this limitation will be noted in any published reports.

The exploratory analyses do not have pre-specified hypotheses and so it is not possible to say how many participants would be required. Cohen (1998) recommends having at least 30 participants in each subgroup. Our large sample size should entail having a sufficient number of participants for these exploratory analyses, and the precise number of participants in each will be specified in any publication.

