## 12b. Statistical methods

As a reminder, the sample-size is designed to support a factor analysis for the hand-hygiene component of the project. The surface cleaning component of the project will only be analyzed using descriptive and exploratory methods.

Software: The data will be analysed using the most recently available copies of SPSS and SPSS: AMOS.

Descriptive: Frequencies, percentages, averages and confidence intervals will be used to describe the participants' responses and demographics.

Internal Consistency: Cronbach's alphas will be calculated. Items will be removed as necessary to achieve an alpha coefficient of 0.70 or above within each domain; those coefficients as low as 0.65 will be tolerated if necessary to retain the planned model.

[figure not shown]
Confirmatory Factor Analyses (CFA) - Objective 4: CFA will be performed to test whether the data from the items fit within the pre-determined components.

The first models (the primary analyses) will be conducted with the data from all the countries and then additional models (the secondary analyses) will be conducted with each country.

The models will be specified in AMOS and tested for goodness of fit using three indices: (a) absolute fit (based on a Chi-squared to degrees of freedom ratio, less than 2; ), (b) parsimony (based on Root Mean Square Error of Approximation (RMSEA) of close to or less than 0.06), and comparative fit (based on an index 'close to' 0.95; ). The models may be revised until the desired measures of fit are obtained.

Figure will be created to describe the final models' structure. An example of a figure like this with only 2 determinates appears below (Figure 2):

Figure 2. Example of a CFA model

Regression analyses - Objective 5: Multiple regression analysis will be conducted, overall and for each country. The predictors will be participants' average responses to each behavioural determinate, and the outcome will be participants' average responses to the confidence items. An alpha value of 0.05 will be used to assess each predictors' contribution to the overall model.

Exploratory Analyses - Objective 6: The participants' individual differences will be compared using graphical analyses (bar charts with error bars) and statistical tests (e.g., ANOVAs). Their content is not further specified within this protocol.

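### Section 12a claims at least 10 participants per parameter with teachers the only exception, but the planned 33-item country CFAs have at most 8.0 in six of the seven countries

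*Combined protocol and SAP*

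**What the plan says.** Section 12a of the combined protocol and SAP states that the sample is sized for the factor and regression analyses of the hand-hygiene component. It adopts a two-part rule of thumb: "collecting responses from 10 to 20 participants for each parameter in the hypothesized model", "with at least 100 participants in each sub-group". It adds that "each domain in the final survey will be captured by at least three items", and concludes: "Our planned samples size meets these criteria, with the exception of teachers and this limitation will be noted in any published reports". It prints no parameter count and no ratio.

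Section 12b makes the pooled CFA primary and then says that "additional models (the secondary analyses) will be conducted with each country". The first secondary hypothesis in section 5b is judged on those country models.

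Two parts of section 12b bear on the parameter count. The factor structure is illustrated only by Figure 2, introduced with "An example of a figure like this with only 2 determinates appears below"; the figure is missing from the available text. Items may also be dropped for internal consistency: "Items will be removed as necessary to achieve an alpha coefficient of 0.70 or above within each domain", with the concession that "those coefficients as low as 0.65 will be tolerated if necessary to retain the planned model".

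**The concern.** A country CFA of the same model has as many free parameters as the pooled CFA but far fewer people: 525/3,975 = 13% of the pooled sample in six countries and 825/3,975 = 21% in India. A ratio that is comfortable when pooled need not hold within a country. Section 12a does not separate the two cases, and the one exception it names is a group of participants, not a set of models.

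At stake is the accuracy of an adequacy statement. A reader weighing the first secondary hypothesis would reasonably take section 12a to say that the country models satisfy the plan's own criterion.

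**Working it through.** **Inputs.**
- Planned sample (section 11, Table 2). Six countries: 225 + 225 + 75 = 525 each. India: 375 + 375 + 75 = 825. Pooled: 6 × 525 + 825 = 3,975.
- Model (Appendix A): 11 domains with three hand-hygiene items each, 11 × 3 = 33 items.
- Criteria (section 12a): at least 10 (up to 20) per parameter, and at least 100 per sub-group.

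**The 100 per sub-group criterion.** This reproduces as stated. Every country has at least 525 people, and mums and dads number at least 225 each in every country. Only the teacher cells, at 75 per country, fall short. Pooled teachers number 7 × 75 = 525, so the exception refers to teachers within a country.

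**Parameter counts.** The plan gives none, so they are derived here, with each item loading on its own domain and no equality constraints.
- Uncorrelated factors: 22 free loadings + 11 factor variances + 33 error variances = 66. This is the minimum for 33 items under these conditions.
- Second-order factor: 66 + 11 second-order loadings = 77.
- All factors correlated: 66 + (11 × 10)/2 = 66 + 55 = 121.

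**Ratio = participants / free parameters.**

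| Structure | Parameters | Six countries (525) | India (825) | Pooled (3,975) | N needed for 10 |
|---|---|---|---|---|---|
| Uncorrelated | 66 | 8.0 | 12.5 | 60.2 | 660 |
| Second-order | 77 | 6.8 | 10.7 | 51.6 | 770 |
| All correlated | 121 | 4.3 | 6.8 | 32.9 | 1,210 |

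Counting 33 item intercepts as well in the correlated model (154 parameters) gives 3.4, 5.4 and 25.8.

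At 10 per parameter, 525 people support at most 52 parameters, which is below the minimum of 66. The six countries pass only if items are counted in place of parameters (525/33 = 15.9), which is not the rule that section 12a states.

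**Country regressions.** These are not in question. Eleven slopes and an intercept give 525/12 = 43.8 per coefficient.

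**The case against.** The strongest reply is that the two criteria have different objects: the ratio belongs to the hypothesized model, in the singular and hence the pooled primary model, and the floor of 100 belongs to sub-groups. On that reading the sentence is true, and teachers are indeed the only exception. The reading has some force. If the ratio bound every country model, a floor of 100 would do no work, because 66 parameters already call for 660 people. The teacher exception shows that the floor was checked within country; it does not show that the ratio was.

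What stands is that this reading is possible. The text does not state it. Section 12a says that the sample supports the factor analysis, and section 12b defines that analysis as pooled and country models. If the narrower scope was meant, it should be written down. It is also fair that no printed figure fails to reproduce, since section 12a prints none.

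A second reply is that item removal would lower the parameter count. It can. Seven items dropped from the uncorrelated model leaves 26 items and 52 parameters, 525/52 = 10.1. A reader might infer that this is the only such route, but section 12b sets no minimum number of domains and allows model revision. For example, a second-order model with ten two-item domains has 2 × 20 + 10 = 50 parameters (525/50 = 10.5), and seven correlated two-item domains have 2 × 14 + 21 = 49 (10.7). These are illustrations, not planned models. They also have limits. An uncorrelated two-item factor has four free parameters and three observed moments, so it is not identified without added constraints. If all 11 domains are kept with two items each, the second-order (525/55 = 9.5) and correlated (525/99 = 5.3) models stay below 10. None of this rescues the planned 33-item model, and fewer than three items departs from section 12a's own standard.

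**Conclusion.** For the country CFAs, the adequacy statement in section 12a is wrong as written, or at best unsupported if a narrower scope was intended. With all 33 items and no equality constraints, the six 525-person countries have at most 8.0 participants per parameter, below 10 under every structure considered. India's result depends on the factor covariance structure, which the readable text does not give. Figure 2 might settle India, but it cannot take the unconstrained 33-item model below 66 parameters. The ratios assume full recruitment. Section 11 lets a country close after 30 days, and section 11b excludes incomplete surveys, so achieved ratios could be lower.

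Three stronger inferences are not supported:
- That the primary analysis is undersized. The pooled model passes under every structure.
- That the country estimates will be unstable. Section 12a itself calls the criterion a rule of thumb, and missing it does not show instability.
- That the plan undertakes to report the teacher limitation and no other. Section 12a says that this limitation will be noted; it does not exclude others.

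**What to change.** Restate section 12a so that the per-parameter criterion is claimed for the pooled model only, and name the country CFAs as a further exception. For example: *The pooled model meets the per-parameter criterion. Country models with all 33 hand-hygiene items do not meet it in the six countries with 525 planned participants (at most 8.0 per parameter), nor in India if all factors are correlated. Teacher groups within country (75) are below 100. Both limitations will be reported.*

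Report the ratio for each country from the fitted model's own parameter count and the achieved sample, so that the published figure does not rest on an assumed structure.

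The change needs no extra participants or analyses. Its cost is a less favourable adequacy statement for the first secondary hypothesis.
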